3.2 STUDY OBJECTIVES & ENDPOINTS

3.2.1 STUDY OBJECTIVE

▶ Primary Objectives: To assess the efficacy of BBL in improving the appearance of senile purpura

Important Secondary Objectives:

- > To assess the safety of a new BBL protocols for treating and preventing senile purpura
- > To assess the long-term efficacy 30 days after all treatments have stopped
- To assess the efficacy of BBL in affecting histological changes such as epidermal thickness
- > To assess the changes in mRNA after treatment

3.2.2 PRIMARY ENDPOINT

➤ Primary Endpoint: Mean absolute difference between the treated and non-treated arms in the change of total square area and number of ecchymoses from baseline to 30 days after the last treatment.

3.2.3 SECONDARY ENDPOINTS

- 1. Measurement of pain, swelling, blistering, erythema, and all side-effects immediately after each procedure, as well as 24 hours, 48 hours, and 7 days after the procedure.
- 2. Mean absolute difference in the number of skin tears at baseline and 30 days after the last treatment
- 3. The changes in collagen and elastin between untreated and treated skin
- 4. Mean absolute difference in the change in epidermal thickness between treated and untreated skin
- 5. Changes in gene expression between treated and untreated skin

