I agree to ensure that all staff members involved in the conduct of this study are informed about their obligations in meeting the above commitments.

Principal Investigator: [name]

_Date: ______ Signature

Title:

A Prospective, Randomized, Split-Arm Clinical Study Investigating the Efficacy and Safety of Sciton's Broad Band for the Treatment and Prevention of Senile Purpura

Précis:

There will be ten subjects, 5 older subjects over 65 years of age with at least one ecchymotic lesion on each arm measuring at least one cm, and 5 subjects under 35 years of age. All subjects will be randomized to undergo 4 Sciton Broad Band Light (BBL) treatments on either their left or right arm one week apart. Subjects will fill out questionnaires, have pictures of their lower arms taken, and will be graded and measured by evaluators regarding the number and size of their ecchymoses as well as side effects such as blistering, pain, erythema, and swelling. One day after their 4th treatment, subjects will have biopsies done to be analyzed for changes in histology and gene expression. The subjects will follow up at 30 days after their last treatments for final pictures of their lower arms and evaluations.

Objectives:

Primary Objectives: To assess the efficacy of BBL in improving the appearance of senile purpura

Important Secondary Objectives:

- 1. To assess the safety of a new BBL protocol for treating and preventing senile purpura
- 2. To assess the efficacy of BBL in reducing skin tears
- 3. To assess the efficacy of BBL to improve the histology of the skin
- 4. To assess the efficacy of BBL to increase epidermal thickness
- 5. To assess the efficacy of BBL to change gene expression

Endpoint

Primary Endpoints:

- Mean absolute difference in the BBL treated arms as compared to the non-treated arms of those with senile purpura in the total square area of purpuric lesions from the first treatment to 30 days after the last treatment
- Mean absolute difference in the BBL treated arms as compared to the non-treated arms of those with senile purpura in the number of purpuric lesions from the first treatment to 30 days after the last treatment

Important Secondary Endpoints:

1. Measurement of pain, swelling, blistering, erythema, and all sideeffects immediately after each procedure, as well as 24 hours, 48 hours, and 7 days after the procedure.

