Subject follow up questionnaires filled out by all subjects

• Study Intervention #4:

Sciton's BBL done a fourth time on the assigned arm according to protocol settings

• Post-Procedure Assessments:

Post-procedure questionnaires filled out by all subjects immediately after treatment

Day 22 +/- 2 Days: Follow-up assessment via skin biopsy

• A 4mm punch biopsy will be done on both the treated and untreated arm approximately 4cm below the crease in the antecubital fossa

Day 51 +/- 2 Days: Follow-up assessment

Follow-up assessments:

Evaluator assessment and measurement

Pictures taken of subject's lower arms

Subjects follow up questionnaires filled out by all subjects

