3 STUDY DESIGN, OBJECTIVES, AND ENDPOINTS

3.1 DESCRIPTION OF THE STUDY DESIGN

- A Prospective, Randomized, Split-Arm Clinical Study
- Single Center
- Study agent: Sciton's BBL
- Study Interventions: BBL Treatment on Day 0, Day 7, and Day 21
- Evaluations on Day 0, Day 7, Day 14, Day 21, Day 22, Day 51.

This will be a prospective, split-arm clinical study in which 5 subjects will be randomized to which arm will be treated with Sciton's BBL.

All subjects will have their arms shaved prior to the procedure and cleaned thoroughly with alcohol. After the procedure a zinc-based sunscreen will be applied to both arms.

Before each of the four treatments and 30 days after the last treatment, the subjects' number and square area of ecchymoses will be measured by an evaluator. Side effects will be measured on Day 0, 1, 2, 7, 14, 21, 22 and 51. Digital photography of subject's arms will be done on day 0, 7, 14, 21, and 51.

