6.2.3 FOLLOW UP TREATMENTS

2nd Treatment (Visit 2, Day 7 +/- 2 days)

- Record adverse events as reported by participant or observed by investigator.
- Subjects fill out adherence questionnaire and evaluator review to ensure continued eligibility
- Evaluator measures the size and number of bruises and number of skin tears
- Shave bilateral lower arms
- Take digital pictures of subjects' lower arms
- Perform the BBL treatment the second time per protocol
- Record adverse events as reported by participant or observed by investigator.
- Perform protocol adherence check by study coordinator
- Expected post-procedure side and post-op written instructions reviewed

3rd Treatment (Visit 3, Day 14 +/-2 days)

- Record adverse events as reported by participant or observed by investigator.
- Subjects fill out adherence questionnaire and evaluator review to ensure continued eligibility
- Evaluator measures the size and number of bruises and number of skin tears
- Shave bilateral lower arms
- Take digital pictures of subjects' lower arms
- Perform the BBL treatment a third time per protocol
- Record adverse events as reported by participant or observed by investigator
- Perform protocol adherence check by study coordinator
- Expected post-procedure side and post-op written instructions reviewed

4th Treatment (Visit 4, Day 21 +/-2 days)

- Record adverse events as reported by participant or observed by investigator.
- Subjects fill out adherence questionnaire and evaluator review to ensure continued eligibility
- Evaluator measures the size and number of bruises and number of skin tears
- Shave bilateral lower arms
- Take digital pictures of subjects' lower arms
- Perform a BBL treatment on the assigned arm a fourth time per protocol
- Record adverse events as reported by participant or observed by investigator.
- Perform protocol adherence check by study coordinator

Expected post-procedure side and post-op written instructions reviewed

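### The side-effect endpoint names no arm, and its delayed readings after treatment 4 coincide with or follow biopsies of both arms, so they cannot be separated from biopsy effects as planned and are mostly unscheduled

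*Combined protocol and SAP*

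**What the plan says.** - **Endpoint.** Section 3.2.3, item 1, reads "Measurement of pain, swelling, blistering, erythema, and all side-effects immediately after each procedure"; it then adds repeat readings one day, two days and one week later. The synopsis at the front of the protocol repeats it. No arm and no comparison are named. Item 3 of the same list shows the contrast in wording: "The changes in collagen and elastin between untreated and treated skin". Items 4 and 5 also compare treated with untreated skin.
- **Treatment 4 and biopsy.** Section 6.2.3 has "4th Treatment (Visit 4, Day 21 +/-2 days". The Précis says "One day after their 4th treatment, subjects will have biopsies done", and the Schematic of Study Design, under Day 22 with a window of 2 days either side, says "A 4mm punch biopsy will be done on both the treated and untreated arm". Section 6.1.2 adds lidocaine and Section 6.2.4 a dissolving suture.
- **Days of measurement.** Section 3.1: "Side effects will be measured on Day 0, 1, 2, 7, 14, 21, 22 and 51". The Visit 5 list in Section 6.2.4 has no side-effect item, and the adverse-effects row of the table in Section 6.2.8 is blank at Day 22.
- **Attribution.** Section 7.2.2 requires other study procedures to be weighed as possible causes. It also lets a temporal relationship alone place an event in the Related category.
- **Preparation of the arms.** Section 3.1: "All subjects will have their arms shaved prior to the procedure and cleaned thoroughly with alcohol". Section 6.2.3 shaves both lower arms at Visits 2 to 4, while Section 6.1.1 speaks of shaving the assigned arm.

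**The concern.** Safety of the new BBL protocol is the first secondary objective listed. A split-arm design supplies a within-subject control for exactly this purpose: background symptoms and biopsy reactions should occur on both arms, BBL reactions on one. Endpoint 1 does not use that control, and Section 8 contains no safety analysis that would bring it in.

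This matters most after treatment 4, when both arms are injected, punched and sutured about a day after the last light session. A subject who reports a sore, swollen or red arm on Day 22 or 23 may be describing either procedure. If answers are not split by arm and site, the delayed safety profile of the last session cannot be read. That session also has the highest ceiling on settings, reached only if every earlier questionnaire was answered NONE.

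**Working it through.** The plan gives no safety rate or sample-size figure to reproduce (Section 8.4 gives none), so the check is calendar arithmetic plus an illustration with assumed rates.

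**1. Nominal reading days** (treatment day + 0, 1, 2 and 7)

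| Treatment | Immediate | 24 h | 48 h | 7 days |
|---|---|---|---|---|
| 1 | 0 | 1 | 2 | 7 |
| 2 | 7 | 8 | 9 | 14 |
| 3 | 14 | 15 | 16 | 21 |
| 4 | 21 | 22 | 23 | 28 |

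With the biopsy on Day 21 + 1 = 22, the readings on or after it are Days 22, 23 and 28. That is 3 of the 4 after treatment 4, 3 of the 4 × 3 = 12 delayed readings, and 3 of all 4 × 4 = 16. No other session is affected.

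**2. Are those readings scheduled?** Section 3.1 lists Days 0, 1, 2, 7, 14, 21, 22 and 51. Of the three affected days only Day 22 is listed, and Sections 6.2.4 and 6.2.8 omit it. Section 7.3 does ask about adverse events at every study visit, which supports Section 3.1, but it sets no order relative to the biopsy and no split by arm. Days 23 and 28 appear nowhere. Days 8, 9, 15 and 16 (24 h and 48 h after treatments 2 and 3) are also unlisted, so 6 of the 12 delayed readings have no listed day.

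**3. Effect of the visit windows.** Take treatment 4 on Days 19 to 23 and the biopsy on Days 20 to 24, independently: 5 × 5 = 25 day-pairs. The gap (biopsy minus treatment) runs from −3 to +5 days, with 1, 2, 3, 4, 5, 4, 3, 2 and 1 pairs.
- 24 h reading on or after the biopsy (gap ≤ 1): 1+2+3+4+5 = 15 of 25.
- 48 h reading (gap ≤ 2): 15+4 = 19 of 25.
- 7-day reading (gap ≤ 7): 25 of 25.
- Both the 24 h and 48 h readings before the biopsy (gap ≥ 3): 3+2+1 = 6 of 25.

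The overlap is therefore complete on nominal days and under the Précis wording, and partial if the windows run freely.

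**4. What can be separated.** Assume a BBL side-effect rate b of 10–50% and a biopsy-site rate p of 20–80% per arm, all independent. These rates are assumptions; the documents give none.
- Not split by arm: 1 − (1 − b)(1 − p)², from 42% to 98%.
- Treated arm alone: 1 − (1 − b)(1 − p), from 28% to 90%.
- Treated minus untreated: b(1 − p), from 2 to 40 points.

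For b = 30%, the unsplit figure is 55%, 83% or 97% as p goes from 20% to 50% to 80%, and the arm difference is 24, 15 or 6 points. The unsplit figure overstates the BBL rate. The arm difference alone understates it, because a biopsy reaction on the treated arm masks a BBL reaction. Hence the need for recording by site as well as by arm.

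**5. Settings at treatment 4** (Section 6.1.1). After three all-NONE results: step 3 is 10 + 3 = 13 J, step 4 is 8 + 3 = 11 J, and step 1 is 10 + 3 × 10 = 40 passes. The same rules can also lead down to 10 − 6 = 4 J and 8 − 6 = 2 J.

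**The case against.** Each procedure in endpoint 1 most naturally means a BBL session, and BBL is given to one arm only, so the arm may be implicit. The side-effect questionnaire is not in the documents and may already have left and right columns. The biopsy is a single 4 mm punch about 4 cm below the elbow crease, so its effects can be told apart by location. Section 2.3.1 lists biopsy risks separately from BBL risks and does not list blistering among them. Section 7.2.2 tells the investigator to consider study procedures as a cause.

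Part of this stands. Blistering is little affected. The immediate reading after treatment 4 precedes the biopsy on nominal days. Site-level separation is feasible, but nothing in the plan calls for it. Section 7.2.2 does not settle the matter: a forearm that is red the day after BBL and just after a biopsy has a temporal relationship (Related) and possibly an established other cause (Not Related). That section also governs adverse-event causality, not the questionnaire answers that endpoint 1 would most naturally draw on.

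A reader might go further and infer that biopsy effects will be charged to BBL. No passage does that. The documents support only that the two cannot be separated as planned. Nor do they support saying that treatment 4 is given at the highest settings; that is a ceiling. Shaving is not part of the biopsy problem either: it is listed at treatment visits and at Day 51, not at Visit 5. It matters only for whether the untreated arm is prepared alike.

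**Conclusion.** The point holds in this form. Endpoint 1 specifies no arm and no comparator, and on nominal days all three delayed readings after treatment 4 fall on or after biopsies of both arms. One of the three is scheduled inconsistently and two are not scheduled at all, so for the last session the delayed readings are either confounded or may not be taken. The extent is limited to 3 of 16 nominal readings, and the primary endpoint is not touched.

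The conclusion assumes that the unseen questionnaire does not already record by arm and site, that the biopsy takes place about one day after treatment 4, and that a punch wound can cause local pain, swelling or redness. Section 2.3.1 does not list those three as biopsy risks, though scarring and infection appear there for both procedures. The documents give no rates, so the size of any distortion is unknown. The correction is cheap and should be made.

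**What to change.** 1. Record every side effect separately for the left and right arm and by site (biopsy site versus the rest of the forearm). Define endpoint 1 as treated-arm incidence, reported with the within-subject treated-minus-untreated comparison at each time.
2. At Visit 5, complete the 24-hour side-effect record before lidocaine is injected. From then on, enter biopsy-site effects on a separate line that is excluded from endpoint 1.
3. Reconcile Section 3.1 with Sections 6.2.4 and 6.2.8 on Day 22, and add the at-home questionnaire for the 48-hour and 7-day readings after treatment 4. The unlisted 24-hour and 48-hour readings after treatments 2 and 3 should be settled in the same edit.
4. Reconcile Section 6.1.1 (assigned arm shaved) with Section 6.2.3 (both arms shaved), so that it is clear whether the untreated arm is a like-for-like comparator.

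The cost is a slightly longer questionnaire, a few minutes at Visit 5, two more at-home forms after treatment 4 (and further forms if the readings after treatments 2 and 3 are collected), and changes of wording. Treatment itself is unchanged.

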4 STUDY ENROLLMENT AND WITHDRAWAL

4.1 PARTICIPANT INCLUSION CRITERIA

In order to be eligible to participate in this study, an individual must meet all of the following criteria:

- Provision of signed and dated informed consent form
- Stated willingness to comply with all study procedures and availability for the duration of the study
- Male or female, aged >22
- In good general health as evidenced by medical history
- Ecchymosis greater than 1cm on each arm

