6.2.2 ENROLLMENT/BASELINE

Enrollment/Baseline Visit (Visit 1, Day 0) Treatment #1

- Review in depth the study design with subjects and obtain informed consent of potential participants verified by signature
- Perform examination and verbally review subject's medications, medical history, and subject questionnaire to determine eligibility based on inclusion/exclusion criteria

- Obtain demographic information
- Shave the hair on the subjects' lower arms
- Take digital pictures of subjects' lower arms
- Have evaluator measure the size and number of bruises and skin tears
- Perform the BBL treatment on assigned arm per protocol
- Record adverse events as reported by participant or observed by investigator
- Perform protocol adherence check by study coordinator
- Expected post-procedure side effects and possible emergent situations reviewed with subjects and post-op written instructions given

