8.4 SAMPLE SIZE

N/A – Pilot Study

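### Secondary endpoint 2 compares skin-tear counts on Day 0 and Day 51 only, names no treated-versus-untreated comparison, and leaves the Day 7, 14 and 21 counts unused

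*Combined protocol and SAP*

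**What the plan says.** The précis lists among its important secondary objectives "To assess the efficacy of BBL in reducing skin tears". The matching endpoint, worded identically in the synopsis and in Section 3.2.3, is "Mean absolute difference in the number of skin tears at baseline and 30 days after the last treatment". Day 51 is 30 days after the last treatment on Day 21. Unlike the primary endpoints and the epidermal-thickness endpoint, this one does not mention the two arms.

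Tears are counted more often than the endpoint needs. On Day 0 the instruction (Section 6.2.2) is "Have evaluator measure the size and number of bruises and skin tears". At Days 7, 14 and 21 (Section 6.2.3), and again at Day 51 (Section 6.2.5), it is "Evaluator measures the size and number of bruises and number of skin tears". Neither Section 6.2.4 nor the schedule of events lists an evaluator measurement at Day 22.

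The only lesion criterion for entry in Section 4.1 is "Ecchymosis greater than 1cm on each arm"; no current or past tear is required. The SAP and Section 8.1 give a method for the primary endpoint only. Section 8.4 gives the sample size as "N/A – Pilot Study". The précis says "There will be ten subjects, 5 older subjects over 65 years of age", the other five being under 35, while Section 3.1 describes a study "in which 5 subjects will be randomized".

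**The concern.** The objective is about how many tears happen. The endpoint compares the numbers recorded on two dates 51 days apart. A tear occurs and then heals, so a two-date comparison can pass over tears that the evaluator recorded in between. Because entry does not depend on having a tear, some arms will probably start at zero, and a before-after measure within such an arm can only stay level or get worse.

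With no arm comparison in the wording, the untreated arm is not used as the control, although the split-arm design provides one. The word absolute is also undefined here: read as an unsigned difference, it would lose the direction of change. At stake is whether the trial can say anything useful about skin tears from data it already plans to collect.

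**Working it through.** The plan gives no tear rate, healing time, alpha or power for this endpoint, so it has no figure to reproduce. The rates and durations below are assumptions.

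**Counts used.** The scheduled counts fall on Days 0, 7, 14, 21 and 51. The endpoint uses 2 of 5. Of the four post-baseline counts, 3 (75%) have no stated use. This step rests on the documents alone.

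**Tears seen at visits but not on Day 51.** Assume that tears start at a constant rate over Days 0 to 51, that each stays visible for *h* days (7 ≤ *h* ≤ 30), that visits fall on their nominal days, and that a visit count means tears present that day. Then:

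- The visits at Days 7, 14 and 21 together cover every onset in Days 0 to 21, which is 21 days.
- The Day 51 visit covers onsets in the last *h* days.
- Share of all tears visible on Day 51 = *h*/51.
- Share seen at any post-baseline visit = (21 + *h*)/51.
- Of those seen at any post-baseline visit, share not seen on Day 51 = 21/(21 + *h*).

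| *h* (days) | Visible on Day 51 | Seen at any visit | Of those, not on Day 51 |
|---|---|---|---|
| 7 | 7/51 = 14% | 28/51 = 55% | 21/28 = 75% |
| 14 | 14/51 = 27% | 35/51 = 69% | 21/35 = 60% |
| 21 | 21/51 = 41% | 42/51 = 82% | 21/42 = 50% |
| 28 | 28/51 = 55% | 49/51 = 96% | 21/49 = 43% |

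The last column exceeds one half only when *h* is below 21 days. The Day 51 count misses more than half of all tears only when *h* is below 51/2 = 25.5 days.

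**Floor at zero.** If the number of tears present on an arm is Poisson with mean *m*, the chance of none is exp(−*m*). If the two arms are independent, the chance that both have none is exp(−2*m*).

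| *m* | One arm at zero | Both arms at zero |
|---|---|---|
| 0.1 | 90% | 82% |
| 0.25 | 78% | 61% |
| 0.5 | 61% | 37% |
| 1.0 | 37% | 14% |

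**What the extra counts could buy.** Paired one-sided t-tests were simulated at an assumed alpha of 0.05, with 5 subjects, a treated-to-untreated tear-rate ratio of 0.5, *m* from 0.25 to 1.0, *h* of 7 or 14 days, and 6,000 runs per setting. Both measures are treated minus untreated.

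| Effect starts | Change from Day 0 to Day 51 | New tears over Days 7, 14, 21, 51 |
|---|---|---|
| Day 0 | power about 7-13% | about 14-44% |
| Day 21 | about 7-13% | about 8-11% |

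The gain is real if the effect is immediate and largely disappears if it begins only after Day 21.

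**The case against.** The strongest reply is that Day 51 is a sensible single time point. It matches the timing of the primary endpoint. Section 2.3.2 expects fewer tears through a thicker epidermis, and Section 2.1 cites mouse work in which collagen and elastic-fibre changes appeared only after three treatments. Days 7 to 21 fall within the treatment course, so counts from those days could dilute a late effect. This stands, and it is why the two periods need separate reporting. It does not explain why the endpoint omits the arm comparison or why the interim counts are collected without a stated use.

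It can also be said that this is a secondary endpoint in a pilot, that skin tears do not appear among the objectives in Section 3.2.1, and that no definition will give more than description with so few subjects. That too stands, and it limits the weight of the point.

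A reader might infer three stronger things that the documents do not support:

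- **That the endpoint discards most tears.** This depends on a healing time the documents do not give. At 21 days of visibility, the Day 51 count holds half of the tears seen at post-baseline visits. Section 2.1 lists delayed healing as a feature of dermatoporosis, so long visibility cannot be excluded.
- **That starting at zero rules out showing a benefit.** It blocks only a decrease within that arm. In a comparison of arms, a subject with no tears on either side at Day 0 can still show a benefit if the untreated arm goes on to gain more tears. The probability of a zero start also moves widely with the assumed rate.
- **That tears between visits are never captured.** The visit sections do not say whether a count means tears present or tears since the last visit. The questionnaire is not in the documents. Section 7.3 has the investigator ask about adverse events since the last visit, although its window for non-serious events closes 7 days after the last intervention, on Day 28 (21 + 7).

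**Conclusion.** The point holds in limited form. What is documented is that the endpoint uses two of five counts, names no treated-versus-untreated comparison, and leaves three of four post-baseline counts without a purpose, in a population not selected for having tears. A before-after comparison on two dates is a weak answer to an objective about reducing tears.

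The size of the loss is conditional. Of the tears seen at post-baseline visits, between 43% and 75% would be missing from the Day 51 count for visibility of 28 down to 7 days, given constant onset and counts of tears present on the day. Any gain in power also depends on the effect starting early. The redefinition is worth making because it costs little and uses the design's own control arm, but it will not turn a descriptive result into a confirmatory one. The primary endpoints are unaffected.

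**What to change.** Redefine secondary endpoint 2, in both the synopsis and Section 3.2.3, as the within-subject treated-minus-untreated difference in the number of new skin tears per arm after Day 0 through Day 51. Then:

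- Use the evaluator counts at Days 7, 14, 21 and 51, and count each tear once by checking it against the previous visit's photographs, starting from those of Day 0. State that this is what a visit count means.
- Report Days 0-21 and Days 21-51 separately, so that a late effect is not hidden by the early counts.
- Keep the between-arm difference in change from Day 0 to Day 51 as a supporting measure. Drop the word absolute or define it so that direction is kept.
- Treat any tears recalled by subjects as descriptive only. No sham is described, so subjects may know which arm was treated.
- State which subjects are analysed, and reconcile the objectives (précis against Section 3.2.1) and the number of subjects (précis against Section 3.1). Describe the result without a claim of significance.

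The cost is endpoint wording, a counting rule and the evaluator's time to match photographs. Counts and photographs are already scheduled on all five days, so no visit is added. Two weaknesses remain. Tears that arise and heal between Day 21 and Day 51 may still be missed: under the assumptions above, (30 − *h*)/51 of all tears, or 45% at 7 days of visibility and 4% at 28. The early counts may also dilute a late effect in the overall total.

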5.1.2 DURATION OF THERAPY

- The BBL treatment will take approximately 15 minutes
- The last treatment will be done on Day 21

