6.2.5 FINAL STUDY VISIT

Follow-up Visit 2 (Visit 6, Day 51 +/-2 days)

- Record adverse events as reported by participant or observed by investigator.
- Subjects fill out adherence questionnaire and evaluator review to ensure continued eligibility
- Evaluator measures the size and number of bruises and number of skin tears
- Shave bilateral lower arms
- Take digital pictures of subjects' lower arms
- Provide final instructions

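### The skin-tear endpoint names two time points but no arm, so read literally it is an uncontrolled before-after change

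*Combined protocol and SAP*

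**What the plan says.** The skin-tear endpoint is secondary endpoint 2. It reads "Mean absolute difference in the number of skin tears at baseline and 30 days after the last treatment", with the same wording in the synopsis list of important secondary endpoints and in section 3.2.3. It serves a synopsis objective, "To assess the efficacy of BBL in reducing skin tears"; the objectives listed in section 3.2.1 leave skin tears out.

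The neighbouring efficacy endpoints are worded differently. The primary endpoint in section 3.2.2 is the "Mean absolute difference between the treated and non-treated arms in the change of total square area and number of ecchymoses". Secondary endpoint 4 is the "Mean absolute difference in the change in epidermal thickness between treated and untreated skin". Secondary endpoints 3 (collagen and elastin) and 5 (gene expression) also name treated and untreated skin.

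At the baseline visit (section 6.2.2) the instruction is "Have evaluator measure the size and number of bruises and skin tears". At the final visit (section 6.2.5) it is "Evaluator measures the size and number of bruises and number of skin tears", and section 6.2.3 has the same step at each later treatment visit. None of these says that the tear count is kept separately for each arm.

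The hypotheses and the paired t-test, in the SAP and again in section 8.1, cover only the number and size of ecchymoses. Section 8.3 adds subgroup analyses of primary and secondary endpoints but no arm comparison. Section 8.4 gives no sample size calculation.

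**The concern.** Skin tears is the only efficacy endpoint whose definition lacks the arm comparison, yet its objective is a causal one. A change from baseline to Day 51 on its own combines any BBL effect with everything else that happened over those weeks.

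The protocol itself puts some shared influences in place: sunscreen on both arms (section 3.1), repeated shaving of both lower arms (section 6.2.3), and a ban on changes in anticoagulant or prednisone use (section 6.3). Natural fluctuation and greater care of the arms while under observation would act in the same way. Whether any of these alters tear counts over this period is not known from the documents. The untreated arm is there so that it need not be known, and the endpoint as worded does not use it.

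At stake is a pilot result on tears that could be read as efficacy, and carried into the planning of a later trial, without having been compared with the control arm.

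**Working it through.** **1. Timing.** Section 5.1.2 (duration of therapy) says "The last treatment will be done on Day 21". 21 + 30 = 51, so the follow-up time in the endpoint is the Day 51 visit.

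**2. Which endpoints name the arms.**

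| Endpoint | Treated vs untreated named? |
|---|---|
| Primary, area and number of ecchymoses (synopsis, 3.2.2) | Yes |
| Secondary 2, skin tears (synopsis, 3.2.3) | No |
| Secondary 3, collagen and elastin | Yes |
| Secondary 4, epidermal thickness | Yes |
| Secondary 5, gene expression | Yes |

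Secondary 1 is a safety measure and is left aside. No text in the SAP or in section 8 supplies the missing contrast for tears.

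**3. What each definition estimates.** For one subject let c be the change shared by both arms, b the BBL effect, and e random error.

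- Treated arm, Day 51 minus baseline: D_T = b + c + e_T
- Untreated arm: D_U = c + e_U
- Literal endpoint, treated arm only: mean of D_T estimates b + c
- Arm contrast: mean of D_T − D_U estimates b

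**4. Illustrative size.** The documents give no figure to reproduce: no test, alpha, tear rate or SD for this endpoint. The following are therefore assumptions: a t-test on the treated-arm changes, approximate normality, b = 0, and c of 0.5 or 1 SD of D_T. The one input from the documents is n = 5, the older group with ecchymotic lesions in the Précis.

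Noncentrality = (c/SD) × √n, with df = 4 and √5 = 2.236. Critical values are 2.132 (one-sided 5%) and 2.776 (two-sided 5%).

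| c/SD | Noncentrality | Rejects, two-sided | Rejects, one-sided |
|---|---|---|---|
| 0.5 | 1.118 | 14.1% | 23.9% |
| 1.0 | 2.236 | 40.1% | 58.0% |

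For D_T − D_U, c cancels, the noncentrality is 0, and rejection is 5% either way.

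**5. Check on counts.** Tear counts are small integers, so a simulation was also run: 40,000 trials per scenario, Poisson counts with gamma subject frailty (shape 4), two-sided 5% t-test and no BBL effect. The mean per arm was assumed to fall equally on both arms, from 2 to 1.5, 2 to 1, 3 to 1.5, 1 to 0.5, or 2 to 0.5. At n = 5 the treated-arm before-after test rejected in 6% to 26% of trials. The arm contrast rejected in 3.9% to 4.8% across all scenarios at n = 5 and n = 10. With no common change (1 to 1), both tests stayed at or below 5%.

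**6. The word absolute.** If it means unsigned, the mean change in the same simulation is about 1.0 tear even when the rate stays at 1 per arm, so an unsigned summary would not show whether tears fell or rose.

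**The case against.** The strongest reply is that the sentence is ambiguous and does not amount to a plan to ignore the control. Elsewhere in the endpoint definitions, a mean absolute difference is one between treated and untreated. The tear sentence says at the two times, where section 3.2.2 speaks of a change from one to the other, so a between-arm difference assessed at two times is a possible reading. The randomised split-arm design points the same way. This stands: it would be too strong to infer that the endpoint cannot show a BBL effect under any reading. It does not remove the point, because the neighbouring endpoints spell the contrast out and an analyst who followed this sentence literally would be compliant.

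Other parts of the reply also stand:

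- A reader might infer that arms would be pooled. Nothing in the documents proposes this.
- A reader might infer that tears are recorded without regard to arm. The documents do not show that. Tears are assessed in the same evaluator step as bruises, which must be recorded by arm for the primary endpoint. The procedures are simply silent.
- Regression to the mean has only indirect support, since entry depends on ecchymosis and not on a tear count.
- Absolute may mean absolute as opposed to percentage. The word is used throughout the document, so it is not a defect particular to this endpoint.
- The rejection rates belong to an assumed test. The one-sided 58% should not be taken as the expected consequence.

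That this is a secondary endpoint in a pilot limits its weight. It does not justify leaving the control out of the definition.

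**Conclusion.** The concern holds as a defect of wording. Taken literally, the skin-tear endpoint is an uncontrolled before-after change that does not answer its own objective, and no other section supplies the arm contrast. The design is sound and the control exists.

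The conclusion rests on comparing the texts and needs no numerical assumption. Its size cannot be fixed from the documents. Under the assumed test with n = 5 and a common shift of 0.5 to 1 SD, false rejection is 14% to 40% two-sided or 24% to 58% one-sided, against about 5% for the contrast. With smaller common changes the excess shrinks, and with none it disappears. The point merits correction but does not threaten the primary analysis.

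**What to change.** In the synopsis and in section 3.2.3, redefine the endpoint as the signed within-subject difference, treated arm minus untreated arm, in the change in number of skin tears between baseline and Day 51. Restrict it to the subjects with senile purpura, as the synopsis does for the primary endpoints. A negative value would then mean fewer tears on the treated arm relative to the control.

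In sections 6.2.2, 6.2.3 and 6.2.5, state that tears are counted and recorded separately for each arm.

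The cost is one sentence in two places and a few words in the visit procedures. No new visit, measurement or subject is needed. It is best settled before baseline data are collected: if any counts were taken without noting the arm, the contrast might not be recoverable.
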